2. BACKGROUND AND RATIONALE

According to the International Children's Continence Society (ICCS), OAB is a syndrome that manifests as urinary urgency, frequently accompanied by frequency and nocturia, with or without urgency urinary incontinence, in the absence of urinary tract infection or any other obvious pathology¹. This common and concerning condition can affect individuals of all ages². Approximately, OAB has been identified with a prevalence of 5-12% in children aged 5-10 years and 0.5% in older adolescents aged 16-18 years¹. OAB may manifest as either OAB-wet, which is characterized by urgency urinary incontinence, or OAB-dry, which is characterized by urgency without

incontinence². Furthermore, it is noteworthy that those with OAB, even without urine loss, experience a reduced quality of life (QoL) compared to those without this condition³. Studies on symptoms related to OAB have revealed that they can significantly impact patients' QoL, with OAB-dry being just as distressing as urinary incontinence. Despite extensive research, the underlying pathological mechanism is not yet fully understood, and its complex etiology has resulted in a variety of treatment options⁴. While behavioral and drug therapies are the primary treatments for OAB, they may not be fully effective in curing the condition for all patients.

The first-line treatment for OAB is SU, which comprises several essential components. These include providing patients with information and demystifying their condition, instructing them on how to resolve lower urinary tract (LUT) dysfunction, offering lifestyle advice, registering symptoms and voiding habits, and providing ongoing support and encouragement through regular follow-up sessions with the caregiver⁵. Anticholinergic medications, also known as antimuscarinics, are commonly prescribed as the first-line treatment for OAB in children who exhibit persistent symptoms despite undergoing SU. Solifenacin succinate is a medication that falls into this category and is primarily employed to alleviate symptoms of OAB, such as urinary urgency, frequency, and incontinence. Although solifenacin succinate has demonstrated efficacy in clinical studies, it may result in common adverse effects, including xerostomia, constipation, blurred vision, and headache^{6,7}. These side effects may pose a challenge to patients' adherence to medication, particularly during prolonged

treatment.

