5.2 Adherence Assessment

Upon enrollment, all participants will be required to complete all relevant intervention treatments, as well as subsequent questionnaire surveys and efficacy assessments, without any interruption to the intervention treatment.

6. STUDY PROCEDURES.

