7.1 Specification of Safety Parameters

Participants were required to take solifenacin and high-dose VDS as part of the study. Anticholinergic side effects, including dry mouth, blurred vision, constipation, and nausea, among others, may occur due to solifenacin use. If any of these symptoms occur, the medication will be discontinued, and the participant will be removed from the study. Over-supplementation of vitamin D can lead to symptoms of vitamin D toxicity, including anorexia, nausea, diarrhea, constipation, irritability, and somnolence. Any occurrence of these adverse drug reactions or serum vitamin D levels exceeding 100 ng/mL will be evaluated as unsafe.

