8. INTERVENTION DISCONTINUATION

If any drug-related adverse effects or worsening of OAB symptoms in children during the intervention period occur, intervention measures should be discontinued. Otherwise, the intervention measures will start eight weeks after enrollment and will continue until the final data collection. At this point, study participants can withdraw their participation from this study.

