9.3.1 Intention-to-treat (ITT) analysis

For outcomes that are continuous variables, which are numerical and can take any value within a range, we will use the ITT approach, which is a way of comparing the groups based on their original random assignment to a treatment, regardless of what treatment they actually received or completed. This helps to avoid bias from factors that may influence the results, such as dropout, which is when subjects leave the study before it ends, or crossover, which is when subjects switch to a different treatment than they were assigned to. The ITT approach is also simpler than other ways of analyzing the data that need to consider whether the subjects followed the treatment as planned or not.

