9.5 Outcomes and data Analyses

We will employ diverse measures to describe the characteristics of our data, depending on their nature. For numerical data that are continuous and can take any value within a range, we will use the mean (the arithmetic average of all values), the SD (a measure of how much the values deviate from the mean), the median (the central value when the data are sorted from the lowest to the highest), and the interquartile ranges (IQRs) (the range containing the middle 50% of data). For non-numerical data that are categorical and can belong to multiple groups or categories, we will use the frequency (the number of occurrences for each category) and the percentile (the proportion of data that falls below a specific value or category).

We will examine our data for any outliers or missing values that could influence our analysis. Outliers refer to values that differ significantly from the majority of the data and may indicate errors or exceptional cases, while missing values are data points that are unavailable or not recorded. Although we will employ effective data collection and management practices, missing values may still occur due to various factors.

To estimate the missing values for continuous data, we will use multiple imputation. This approach replaces the missing values with plausible estimates based on the other available data. We will assume that the missing values are missing completely at random, meaning that their occurrence does not depend on any variable, including their value. We will also conduct a sensitivity analysis to determine if the missing values affect our results or conclusions.

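### Removing children from the study for any listed solifenacin side effect leaves their later diaries to be imputed, under a missing-completely-at-random assumption that the rule itself contradicts

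*Combined protocol and SAP*

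**What the plan says.** Section 7.1 lists dry mouth, blurred vision, constipation, nausea and other anticholinergic effects, and then states: "If any of these symptoms occur, the medication will be discontinued, and the participant will be removed from the study". This gives two consequences, stopping the drug and leaving the study, and sets no grade of severity. Section 2 says of solifenacin that "it may result in common adverse effects, including xerostomia, constipation, blurred vision" and headache.

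For vitamin D symptoms, section 7.1 says only: "Any occurrence of these adverse drug reactions or serum vitamin D levels exceeding 100 ng/mL will be evaluated as unsafe". Section 8 covers all arms: "If any drug-related adverse effects or worsening of OAB symptoms in children during the intervention period occur, intervention measures should be discontinued". It does not say whether the child stays in the study. Section 5.2 expects every participant to complete treatment and assessments "without any interruption to the intervention treatment".

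On the analysis side, section 9.3.1 defines intention-to-treat (ITT) for continuous outcomes as "comparing the groups based on their original random assignment to a treatment, regardless of what treatment they actually received or completed". Section 9.5 adds: "To estimate the missing values for continuous data, we will use multiple imputation". It continues: "We will assume that the missing values are missing completely at random", which it explains as missingness unrelated to any variable. It also promises a sensitivity analysis for missing values but gives no method.

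**The concern.** An ITT comparison that disregards treatment completion needs outcomes from children who stopped treatment. The 7.1 rule ends their participation at the moment they stop, for a reason caused by the assigned drug. A child removed before Week 4 has no diary at either follow-up; one removed after Week 4 has none at Week 8. Those values must be imputed, and the information for doing so comes mainly from children who tolerated solifenacin and kept taking it.

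If children taken off the drug lose some of its benefit, imputation gives them values that are too favourable. The error falls in the SOL+SU arm, which enters two of the three pairwise comparisons. One of them is VDS+SU versus SOL+SU, where section 9.1 expects VDS+SU to be superior.

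The rule also merges two events that section 9.5.3 should keep apart. For solifenacin, stopping the drug and leaving the study become the same thing, so the listing of adverse events that led to leaving the study partly reflects the rule itself.

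**Working it through.** **The plan's own figure.** The plan gives no figure for side-effect removals. Its nearest one is the 10% attrition allowance in 9.2: 87/0.90 = 96.7, rounded up to 97 per group, which reproduces.

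**Inputs from the documents (9.2).** Design difference 1.5 voids/day; SD 5.0; 87 per group analysed, 97 recruited.

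**Assumptions (not in the documents).**
- Share p of SOL+SU removed: 5%, 10% or 20%.
- Gap d at Week 8 between removed children off drug and retained children: 1.5 voids/day (the whole design difference), or 0.75.
- Correlation ρ between any two of baseline, Week 4 and Week 8: 0.5.

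**Step 1. Does the rule fit the assumption?** Section 9.5 takes missingness to be unrelated to any variable. Under 7.1 it depends on arm and on tolerability. The two cannot both hold.

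**Step 2. Bias if imputation recovers nothing.** Bias = p × d.
- d = 1.5: 0.05 × 1.5 = 0.075; 0.10 × 1.5 = 0.15; 0.20 × 1.5 = 0.30 voids/day.
- d = 0.75: 0.0375; 0.075; 0.15 voids/day.

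**Step 3. How much can imputation recover?** With baseline and Week 4 as predictors and equal correlations, the regression weight on Week 4 is ρ/(1+ρ). If the Week 4 diary already shows the whole gap, that share of it is recovered: 0.5/1.5 = 0.33. The bias left is p × d × (1 − 0.33), that is 0.05, 0.10 and 0.20. At p = 10%, ρ = 0.3 recovers 0.23 and leaves 0.115; ρ = 0.7 recovers 0.41 and leaves 0.088.

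Simulation check: 3,000 runs, 97 children, normal-regression multiple imputation with 5 imputations, d = 1.5, ρ = 0.5, Monte Carlo SE 0.002 to 0.005.

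| Data available for removed children | p = 5% | p = 10% | p = 20% |
|---|---|---|---|
| Baseline diary only | 0.075 | 0.150 | 0.299 |
| Week 4 diary recorded before the gap appears | 0.075 | 0.152 | 0.299 |
| Week 4 diary already showing the full gap | 0.045 | 0.095 | 0.199 |

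Entries are the bias of the SOL+SU mean, in voids/day, against full follow-up. If baseline severity explains part of the gap, more is recovered.

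**Step 4. Scale.** SE of a difference = 5 × √(2/87) = 0.758. At 10% removal, 0.10 to 0.15 voids/day is 0.13 to 0.20 SE. At 20%, the upper value of 0.30 is 0.40 SE. As a share of the 1.5 design difference, p × d is 5%, 10% and 20%.

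**Step 5. Direction.** Fewer voids is better, and the imputed SOL+SU mean is too low. If VDS+SU is better, as 9.1 expects, its advantage over SOL+SU shrinks by this amount. An advantage of SOL+SU over SU grows by the same amount.

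**The case against.** The strongest reply is that a false assumption of missing completely at random does not by itself bias the result. Multiple imputation needs only that data are missing at random given the variables in its model. That is correct, and it makes the direction of bias conditional: removed children must do worse than the imputation predicts. But section 9.5 specifies no imputation model, and under the 7.1 rule few or no off-drug outcomes would exist to inform one. The planned sensitivity analysis could help, but it is undefined and not tied to these removals.

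One could also read removal as leaving treatment only. The same sentence already stops the drug, so that reading makes its second half redundant. That diaries end remains an inference, though no section contradicts it.

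A reader might infer several stronger points that the documents do not support:
- *That removed children leave the ITT set, or that the whole ITT comparison rests on imputation.* Section 9.3.1 keeps them in their assigned group. Only their missing visits are imputed; retained children contribute observed data, and a child removed after Week 4 keeps that value.
- *That the vitamin D arm has a more lenient rule.* Removal there is unstated, not excluded. Section 8 stops the intervention in any arm, and 5.2 applies to everyone. This is a gap in drafting, not a demonstrated difference between arms.
- *That adverse events go uncounted.* Section 9.3.3 keeps every child with at least one dose and safety records. Only the listing of events that led to leaving the study is affected.
- *That the attrition allowance settles the matter.* It protects precision, since 10% removal from 97 leaves 87. It does nothing about bias.

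**Conclusion.** The concern holds as a minor point. The removal rule conflicts with the missing-data assumption in 9.5 and gives up outcome data that the ITT comparison in 9.3.1 needs. With 5%, 10% or 20% of SOL+SU removed and a 1.5 voids/day gap, the SOL+SU mean would be biased by about 0.05–0.075, 0.10–0.15 or 0.20–0.30 voids/day. The ranges run from a Week 4 diary that already shows the whole gap to one that is absent or uninformative. The largest value is about 0.4 SE, and a gap of 0.75 halves every figure.

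The conflict between sections is certain from the text. The size and direction of bias are not: they rest on an assumed removal rate, gap and correlation. For VDS+SU versus SOL+SU the expected distortion works against the trial's own hypothesis, so a reader should not infer that the rule favours vitamin D.

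**What to change.** - **Sections 7.1 and 8, all arms, every stopping reason (drug-related adverse effect or worsening OAB symptoms).** Suggested wording: *The study drug or intervention is stopped. Unless consent is withdrawn, the child stays in the study, completes the bladder diary and the scheduled Week 4 and Week 8 visits, and is analysed in the assigned group.*
- **Section 5.2.** Align it, so that stopping treatment does not end assessments.
- **Section 9.5.** Replace missing completely at random with missing at random given arm, earlier diary values and treatment discontinuation. Define the sensitivity analysis as delta-adjusted for values still missing.
- **Section 9.5.3.** Report discontinuation of study drug separately from withdrawal from the study.

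The cost is wording plus slightly more follow-up of children who are off treatment, at visits already in the 6.1 schedule. Safety is unchanged, because the drug still stops.

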7.2 Methods and Timing for Assessing, Recording, and Analyzing Safety Parameters

Enrolled participants will undergo follow-up visits every four weeks. These visits

will include a questionnaire and physical examination to assess any drug-related adverse effects, as well as a test of their serum vitamin D levels. In case any adverse effects arise, safety parameters will be promptly evaluated.

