6.1 Schedule of Evaluations

Assessment	Enrollment: Day1	Run-in period (Day2-8)	Week 4 (Day 33- 39)	Week 8 (Day 61-67)
Informed Consent Form	\checkmark			

Efficacy and Safety of High-Dose Vitamin D Supplementation for Overactive Bladder Dry in Children: A Randomized Clinical Trial (Edition Number:3)

Demographics	\checkmark			
Medical History	\checkmark		\checkmark	\checkmark
SU	\checkmark		\checkmark	\checkmark
Bladder Diary		\checkmark	\checkmark	\checkmark
Current Medications		\checkmark	\checkmark	\checkmark
measurements of biochemistry.	\checkmark			\checkmark
measurements of hematology,	\checkmark			\checkmark
measurements of urinalysis.	\checkmark			\checkmark
Adverse Events			\checkmark	\checkmark

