7. SAFETY ASSESSMENTS

This study includes clinical interventions, and the primary focus of safety evaluation will be on assessing the adverse effects and exacerbation of clinical symptoms after oral administration of the drug. Patients will be encouraged to report any related complications or adverse events directly to us.

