9. STATISTICAL CONSIDERATIONS

9.1 General Design Issues

Objective: The aim of this randomized controlled trial is to examine the effectiveness and safety of high-dose VDS plus SU for managing OAB-dry symptoms in pediatric patients with low vitamin D levels (<35ng/mL).

Specific Aim 1: The main outcome is the difference in post-treatment improvement between children who receive high-dose VDS plus SU and those who receive solifenacin plus SU or SU monotherapy for OAB-dry symptoms. The study expects that high-dose VDS plus SU will lead to more improvement than SU monotherapy and solifenacin plus SU. Furthermore, SU monotherapy will result in less improvement than solifenacin plus SU.

Specific Aim 2: The secondary outcome is the safety profile of high-dose VDS plus SU for OAB-dry symptoms in pediatric patients. The study anticipates that the safety profile of high-dose VDS plus SU will be similar to that of solifenacin plus SU or SU monotherapy at follow-up.

The study design is an 8-week randomized controlled trial, and all treatments will be administered in a group setting. Pediatric patients with OAB-dry symptoms will undergo 8 weekly sessions of high-dose VDS plus SU, solifenacin plus SU, or SU monotherapy. Independent assessors will evaluate the patients before the treatment, at mid-treatment (4-week follow-up), and at the 8-week follow-up to test the expectations. To account for attention, time, and group effects, all SU sessions will be administered in a group setting.

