9.5.3 Safety analysis

The safety analysis will be performed using the Safety Analysis Set, which will assess treatment-emergent adverse events (TEAEs). Detailed recordings of all severe adverse events and TEAEs leading to discontinuation from the study will be included. Changes in clinical laboratory parameters and vital signs at each scheduled time point from baseline will be summarized according to treatment groups.

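### Section 7.2 seeks drug-related effects at visits while the schedule, 7.4 and 9.5.3 cover adverse events of any cause, so background symptoms in SU-alone children risk being under-recorded

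*Combined protocol and SAP*

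**What the plan says.** Section 7.2 puts all arms on the same visit schedule ("Enrolled participants will undergo follow-up visits every four weeks") and says that the visits "will include a questionnaire and physical examination to assess any drug-related adverse effects". The questionnaire itself is not given.

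Other sections share the drug-related framing. Section 7 puts the main focus of safety evaluation on "assessing the adverse effects and exacerbation of clinical symptoms after oral administration of the drug". Section 7.1 lists expected symptoms separately for solifenacin and for vitamin D; the second list reads: "Over-supplementation of vitamin D can lead to symptoms of vitamin D toxicity, including anorexia, nausea, diarrhea, constipation, irritability, and somnolence". Section 7.3 describes events as side effects of the two drugs, and 9.4 limits serious adverse events to those related to the intervention.

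Other places have no such filter. The schedule in 6.1 has a row headed "Adverse Events", ticked at Weeks 4 and 8 for everyone. Section 7.4 requires notification of any adverse event. Section 9.5.3 analyses treatment-emergent adverse events (TEAEs) without a relatedness condition and summarizes laboratory and vital-sign changes by arm.

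Specific Aim 2 in 9.1 expects that "the safety profile of high-dose VDS plus SU will be similar to that of solifenacin plus SU or SU monotherapy". The safety set in 9.3.3 requires at least one dose of study drug.

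**The concern.** A comparison with a no-drug arm needs events of any cause, sought in the same way in every arm. Nausea, constipation, diarrhea and irritability also occur in children who take no study drug. If staff record only what they think a drug caused, the SU-alone count is pushed towards zero by construction, and the contrast with SU no longer describes the excess risk of vitamin D.

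No placebo is described, and the blinding in 6.2.3 covers assessors and statisticians. Families therefore know the treatment and may volunteer symptoms more readily when a drug is being taken.

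This is separate from the safety-set definition. Read literally, 9.3.3 leaves out SU-alone children. Correcting it would admit them to the analysis but could not restore symptoms that nobody wrote down.

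**Working it through.** **1. Which text governs collection.**

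| Section | Step covered | Filter on cause? |
|---|---|---|
| 6.1 | timing of the adverse-event record | no |
| 7.2 | how events are sought at visits | yes, drug-related |
| 7.3 | description and grading of events | framed as drug side effects |
| 7.4 | notification of a known event | no |
| 9.4 | definition of a serious event | yes, related to the intervention |
| 9.5.3 | analysis of TEAEs | no |

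The unfiltered sections cover timing, notification and analysis. The one that covers active elicitation is filtered. Nothing says that relatedness is to be recorded as a separate item.

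**2. The symptom lists in 7.1.** Solifenacin: dry mouth, blurred vision, constipation, nausea (an open-ended list). Vitamin D: anorexia, nausea, diarrhea, constipation, irritability, somnolence. Nausea and constipation are on both, so the union has 4 + 6 − 2 = 8 symptoms. No baseline check of these symptoms is specified, although medical history is taken at enrollment and chronic constipation is an exclusion.

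**3. Size.** The plan gives no event rate, margin or power for safety, so there is no safety figure to reproduce. The only design input used is 97 per arm (9.2), which follows from 87 / (1 − 0.10) = 96.7, rounded up.

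Assume the same true 8-week risk b of any listed symptom in vitamin D plus SU and in SU alone. Let cV and cS be the fractions recorded in the two arms. Then:

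spurious difference = b × (cV − cS)

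The last column is the chance of p < 0.05 if someone applied a two-sided Fisher exact test at 97 per arm. The plan specifies no such test.

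| b (assumed) | cV | cS | Expected recorded events | Spurious difference | Chance of p < 0.05 |
|---|---|---|---|---|---|
| 5% | 1 | 1 | 4.9 v 4.9 | 0 | 2% |
| 5% | 1 | 0.5 | 4.9 v 2.4 | 2.5 points | 6% |
| 5% | 1 | 0 | 4.9 v 0 | 5 points | 36% |
| 10% | 1 | 1 | 9.7 v 9.7 | 0 | 3% |
| 10% | 1 | 0.5 | 9.7 v 4.9 | 5 points | 18% |
| 10% | 1 | 0 | 9.7 v 0 | 10 points | 93% |

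Example: b = 10%, cV = 1, cS = 0.5 gives 0.10 × (1 − 0.5) = 0.05, with 97 × 0.10 = 9.7 events against 97 × 0.05 = 4.85.

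If the filter also loses half of the vitamin D events and all of the SU events, the difference is 0.5 × b, that is 2.5 or 5 points.

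**The case against.** A reader might infer that events are collected only if drug-related, that the SU background rate is therefore not captured, and that the comparison is biased. The documents do not support that. The schedule and 7.4 cover adverse events without a filter, and 9.5.3 analyses TEAEs whatever their cause. Section 7 adds "Patients will be encouraged to report any related complications or adverse events directly to us", although there the word "related" may qualify both nouns. Laboratory and vital-sign summaries by arm need no attribution.

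A reader might also infer that each child is asked only about the symptoms of his or her own drug. Nothing says so. Section 7.2 gives the questionnaire to all enrolled children, 7.1 lists what each drug may cause and is not the form, and 10.1 has questionnaires administered blind to arm. A blinded evaluator cannot choose a list by arm or discount nausea because the child takes no drug.

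The zero-capture rows above are a worst case that these provisions make unlikely. No between-arm safety test or margin is planned, so the p-values describe no planned decision. Under-recording in SU would also make vitamin D look less safe than SU, so in that comparison it cannot create false reassurance.

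All of this stands against the stronger readings. It does not remove the conflict. A blinded evaluator told to look for drug-related effects has no sound basis for judging relatedness, and blinding does not reach what families choose to report. Since the form is not shown, equal capture cannot be assumed either.

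**Conclusion.** The point holds as an internal inconsistency that creates a risk of differential recording. Section 7.2, echoed in 7, 7.3 and 9.4, aims at drug-related effects, while 6.1, 7.4 and 9.5.3 need or imply events of any cause. The risk falls on the Aim 2 comparison with SU alone.

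Its size cannot be computed from the documents. It ranges from no distortion under equal capture to the whole background rate if no SU events are recorded: up to 5 points at an assumed 5% and 10 points at an assumed 10%. These figures rest on equal true risks and full recording in the vitamin D arm. What is affected is a by-arm comparison without a formal test. The plan should still be changed, because the change is cheap and events not collected cannot be recovered at analysis.

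**What to change.** Amend 7.2 and 7.3 so that:

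- one checklist, the union of the two symptom lists in 7.1, is asked in identical form in all three arms at baseline, Week 4 and Week 8, by evaluators blind to arm as 10.1 already plans;
- every new or worsened symptom is recorded regardless of suspected cause, with relatedness as a separate field.

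In 9.5.3, report all-cause TEAEs by arm first and drug-related events second. In 9.3.3, word the safety set so that SU-alone children are included.

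The cost is one common form at visits that already exist, a baseline tick list, and more minor events to record. No dose or treatment rule changes.
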